11. Safety Assessment	34
11.1. Definition.....	34
11.2. Adverse Event Collection and Reporting.....	35
11.3. Suspected Unexpected Serious Adverse Reaction (SUSAR) Report.....	36
12. Monitoring	37
12.1. Installation of Data and Safety Monitoring Board (DSMB)	37

Confidential

MDR-END v14.0, 20Mar2020

12.2.	Monitoring Plans	37
13.	Ethical Considerations of the Study.....	38
13.1.	Compliance of Study Ethical Regulations	38
13.2.	Obtaining written informed consent from Subjects	39
13.3.	Protection of Personal Records.....	40
13.4.	Compensation and Indemnities Provided to Subjects.....	40
14.	Administrative Requirements	41
14.1.	Change of Study Protocols	41
14.2.	Subject identification log and screening/enrollment log.....	41
14.3.	Completing Case Report Forms (CRF).....	41
14.4.	Quality Assurance of Data	41
14.5.	Storage of Records.....	42
14.6.	Completion and Stopping the Study	42
15.	References	43

Confidential

MDR-END v14.0, 20Mar2020

Summary of Research Plans

1. Background

Tuberculosis, and especially drug-resistant tuberculosis, is a huge threat to public health not only in Korea, but throughout the world. Treatment of multidrug-resistant tuberculosis (MDR-TB), which exhibits resistance to the two most powerful drugs, must use second-line anti-TB drugs. However, usage of the conventional second-line anti-TB drugs not only has low success rates, but is also accompanied by a range of issues such as side effects due to prolonged use of drugs for about two years for treatment, low compliance, and high costs. Therefore, by developing new treatment regimens for MDR-TB treatment including recently introduced new drugs to improve the treatment efficacy and shortening the therapy period, it will be possible to increase treatment compliance, and consequently raise the treatment success rate.

2. Purpose

This clinical trial is to compare the efficacy of a ‘new treatment regimen including delamanid, linezolid, levofloxacin, and pyrazinamide for nine or twelve months (investigational arm)’ and ‘the standard treatment regimen including injectables for 20 to 24 months (control arm)’ for treating fluoroquinolone sensitive multidrug-resistant tuberculosis.

3. Design of the Study

Multicenter, randomized, open-label, two arms, phase II/III clinical trial

① Group 1 (Control arm)

Minimum 20 months treatment according to the 2014 Korean guidelines for the treatment of tuberculosis and 2014 World Health Organization (WHO) guidelines

② Group 2 (Investigational arm)

Treatment regimen made up of only oral medication using delamanid, linezolid, levofloxacin, and pyrazinamide, and treatment duration of nine months or twelve months depending on the time to sputum culture conversion to negative.

4. Outcomes

The primary outcome is the treatment success rate at 24 months after the initiation of treatment. The secondary outcomes are the time to sputum culture conversion to negative on liquid and solid media after the initiation of treatment, the proportion of participants with sputum culture conversion at 2 and 6 months of treatment on liquid and solid media, and the occurrence of adverse events grade of 3 and higher, proportion of participants with a treatment success at the end of treatment, proportion of relapse after treatment success, proportion of deaths and time-to-death, comparison of treatment success rates between treatment groups according to pyrazinamide resistance.

5. Expected Effects

Confidential

MDR-END v14.0, 20Mar2020

If it is proven that the new treatment regimen is not inferior to the existing treatment regimens through this trial, it will be an epochal opportunity for treating MDR-TB in nine months or twelve months, which is a year shorter than the current 20 to 24 months.

Moreover, by reducing the ‘time to *Mycobacterium tuberculosis* (MTB) culture conversion to negative’ of the current treatment, it will be possible to reduce the transmission of tuberculosis from patients to others.

1. Background of the Study

[figure not shown]
1.1. Prevalence of and Threat Posed by MDR-TB

Multidrug-resistant tuberculosis (MDR-TB) is tuberculosis that is resistant to at least isoniazid and rifampicin, the two most important anti-TB drugs, and it accounts for 3.5% of newly diagnosed TB patients in the world and 20.5% of patients who have been treated in the past. In 2013, approximately 480,000 people were diagnosed with MDR-TB, and approximately 9% of the cases are extensively drug-resistant tuberculosis (XDR-TB) against the conventional TB drugs.(1)

In 2013, there were 951 patients reported with MDR-TB (2), but considering the drug resistance rate in Korea, it is estimated that there are actually about 2,000 new MDR-TB cases occurring in Korea annually.

1.2. Difficulties with Treatment of MDR-TB

In order to treat MDR-TB, second-line anti-TB drugs including injectables must be used for 18-24 months, but the success rate of treatment has recently been reported as 83.7% in Korea (3). It is only 32.2% to 62.0% in other parts of the world (4,5). The WHO estimates the average treatment success rate of MDR-TB to be approximately 48% (Figure 1).

Furthermore, there is a report about frequent side effects of using these second-line drugs that commonly have side effects for usage over long periods of time. And 30% of the 818 MDR-TB patients, or 245 patients, had to stop use of drugs because of adverse drug reactions such as nausea/vomiting, diarrhea, joint pains, dizziness, hearing difficulty, headache, and sleep disorders. (6)

A considerable amount of money is used for treating MDR-TB patients. In the case of Korea, it costs 7-22 times more to treat MDR-TB patients than drug-susceptible TB patients. The expenses needed to treat MDR-TB are similar to that for treating malignant diseases, and thus depletes huge amounts of money.(7, Figure 2)

[figure not shown]

Figure 2 Comparison of the annual cost of multidrug-resistant tuberculosis (MDR-TB) with that of malignant disease in South Korea. All costs demonstrated in this figure are the National Health Insurance Programme-covered annual costs converted to 2004 US dollars.

1.3. Introduction of New Anti-TB Drugs

A few new anti-TB drugs have been clinically introduced recently. These include drugs like moxifloxacin and linezolid which were developed originally to treat ordinary bacterial infections and were found to have strong anti-TB effects, and a few others developed to targeting *Mycobacterium tuberculosis* (MTB) such as bedaquiline, delamanid and PA-824. Research has been conducted on moxifloxacin to evaluate whether it can reduce the treatment period of drug-susceptible TB patients,(8, 9) and it is also reported that linezolid (10,11), bedaquiline,(12) delamanid (13) can improve the treatment outcomes of MDR-TB patients.

In the case of linezolid, it was administered to extensively drug-resistant TB (XDR-TB) patients who did not report improvement with any drugs. Treatment using linezolid showed powerful anti-TB effects obtaining sputum culture conversion to negative in 87% of these patients after six months of treatment (10). The focus of studies is now on how to use linezolid for MDR-TB patients, instead of administering to only XDR-TB patients.

As strong anti-TB medications, such as delamanid and linezolid, were introduced, [name] of the International Union Against Tuberculosis and Lung Disease (IUATLD) suggested a new classification (14). Based on the new classification by [name], the regimen with shorter treatment duration consisted of delamanid, linezolid, levofloxacin, and pyrazinamide.

2. Rationale

2.1. Shortening of Treatment Duration

The main reason for treatment failure in MDR-TB is that patients stop taking their treatment voluntarily for various reasons prematurely. From 1988 to 1996, 342 (39.0%) of 1,175 MDR-TB patients that received treatment at the TB Clinic of Korean National Tuberculosis Association stopped treatment arbitrarily prior to treatment completion (15), and 453 (32.2%) of 1,407 patients who received treatment at eight university hospitals and two national TB hospitals between 2000 and 2002 arbitrarily stopped treatment. (16)

Thus, shortening the treatment duration that currently lasts 24 months is necessary to solve the MDR-TB issue.

There was a recent report that 427 MDR-TB patients in Bangladesh participated in a study and received seven anti-TB drugs including kanamycin and gatifloxacin for 9months. The study reported a cure rate of 82.5%, but 39.8% of participating patients complained of side effects which revealed the difficulties of taking medicine (17).

2.2. Improvement of Treatment Efficacy

Even after treatment failure, MDR-TB patients live for several years and continuously spread MDR-TB bacilli to people they come in contact with. Considering this, it is necessary to raise the treatment success rate that is currently at 48~83.7% to solve the issues pertaining to MDR-TB.

It is expected that MDR-TB patient treatment success rate could be improved by using linezolid that was introduced to treat vancomycin resistant bacterial infection or using the newly developed anti-TB drugs like delamanid and bedaquiline. The biggest interest for now is on how to use it together with current anti-TB drugs.

In other words, the most urgent task is to investigate how to combine existing second-line anti-TB drugs such as fluoroquinolone, with the new drugs such as linezolid, delamanid and bedaquiline for treatment use.

2.3. Contribution to International Community through Research on MDR-TB

It is widely known that Korea has excessively high TB incidence for its economic level.

[figure not shown]

Figure 1. TB Incidence rates by OECD member country, 1990 and 2011

Source : Global Tuberculosis Control WHO Report 2012

The annual TB incidence rate of Korea in 2013 was 97 per 100,000, which is much higher than the rates for Japan (18 per 100,000) and the United States (3.3 per 100,000) (1).

Although the incidence of tuberculosis is shameful, it is also true that a world-class medical environment and excellent researchers provide an appropriate research environment that can lead to innovation in tuberculosis treatment.

It will be a considerable contribution to the international community to solve the burden on public health caused by TB, especially by MDR-TB, as investigators can get meaningful research conclusions through this clinical trial in Korea.

Confidential

MDR-END v14.0, 20Mar2020

3. Previous Research Results

3.1. Comparison of Levofloxacin versus Moxifloxacin for Multidrug-Resistant Tuberculosis

As a coordinating principal investigator, [name] is an experienced researcher who oversaw the present clinical trials for comparing the efficacy of levofloxacin versus moxifloxacin for the treatment of MDR-TB patients. The study was conducted in a prospective, multicenter, randomized trial format from February 2010 to July 2012 with cooperation of 19 domestic institutes in total supported by the Korean Academy of Tuberculosis and Respiratory Diseases. (Clinicaltrial.gov Enrollment Number; NCT01055145)

The purpose of this study was to compare the efficacy between levofloxacin and moxifloxacin, two most commonly used fluoroquinolones which should be included in MDR-TB treatment regimen. A total of 182 MDR-TB patients participated in this study, 88.3% of the levofloxacin group and 90.5% of the moxifloxacin group converted culture to negative at three months of treatment, which showed no difference between the two groups. This result was published in the American Journal of Respiratory and Critical Care Medicine. (18)

3.2. Substitution of ethambutol with linezolid during the intensive phase of treatment of pulmonary tuberculosis

The principal investigator is conducting a research, supported by the Korean Health Industry Development Institute, to investigate whether substituting linezolid for ethambutol can accelerate sputum MTB culture conversion to negative for the treatment of drug-susceptible TB patients. This prospective, multicenter, randomized clinical trial is being joined by Seoul National University, Bundang Seoul National University Hospital, Boramae Hospital, and the National Medical Center. (Clinicaltrial.gov Enrollment Number; NCT1994460)

4. Purpose of the Study

This is a multicenter, randomized, open-label, two arms, phase II/III clinical trial to compare the effects of ‘new treatment regimen including delamanid, linezolid, levofloxacin, and pyrazinamide for nine or twelve months for fluoroquinolone-sensitive MDR-TB (investigational arm)’ and ‘standard treatment regimen including injectables for 20 to 24 months (control arm)’. The purpose of this study is to verify that the success rate of the simpler and shorter treatment is not inferior to conventional treatment.

5. Design of the Study

5.1. Study Design

5.1.1. Study Drug

Investigational drugs (delamanid: Otsuka Pharmaceutical, linezolid: Pfizer Pharmaceutical), provided for free from pharmaceutical companies for this study, will be delivered to the sites after labeling at Otsuka and Seoul National University Hospital according to investigational product labeling regulations. The study drugs will be managed by the designated pharmacists at each site, and stock, storage, dispensation, and return will be recorded in research documents.

① Linezolid

- Brand Name: Zyvox Tab (Pfizer Korea)
- Form: White capsule shaped, film coated tablet
- Composition: linezolid 600mg
- Dosage and administration: Take one tablet (600mg) every day
- Storage method: Stored in a sealed container at room temperature (15 - 30°C)
- Expiration date: 36 months from the manufactured date

② Delamanid

- Brand Name: Deltyba Tab (Otsuka Korea), 50mg
- Form: Yellow, round film-coated table (engraving: DLM, 50)
- Composition: Delamanid 50mg
- Dosage and administration: Take 100mg twice a day together with meal

- Storage method: Stored in a sealed container at room temperature (1 - 30°C)
- Expiration date: 60 months from the manufactured date

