Regimen consists of only oral medication using delamanid, linezolid, levofloxacin, and pyrazinamide, for nine or twelve months.

- Treatment duration

- A total of 9 months (40 weeks) when sputum culture conversion to negative occurs within three months of treatment
- A total of 12 months (52 weeks) when sputum culture conversion to negative occurs between 3 and 6 months of treatment

- Combination of treatment regimen

- Delamanid, 200mg/day (100mg bid)
 - Use for the entire treatment period unless it must be stopped for reasons such as adverse events.
- Linezolid
 - 600mg/day during the first two months
 - 300mg/day afterwards until the end of treatment

Confidential

MDR-END v14.0, 20Mar2020

- If linezolid re-administration is required after temporary discontinuation due to adverse events, the dose reduction to 300mg is allowed even within two months of treatment.
- Levofloxacin
 - $\leq 50\text{kg}$, 750mg/day
 - $>50\text{kg}$, 1000mg/day
 - Can be reduced or substituted with moxifloxacin due to reasons such as adverse events, and at this time, QT prolongation should be observed closely. Also, this substitution will not be considered as a drug change since both are fluoroquinolones of similar potency.
 - Once a day
- Pyrazinamide
 - $<50\text{kg}$, 1000mg/day
 - 50-70kg, 1500mg/day
 - $>70\text{kg}$, 2000mg/day
 - Can be reduced due to adverse event. Even if pyrazinamide resistance is discovered on the phenotypic drugs susceptibility testing after commencing treatment, it can be continued (20).
 - Once or divide in two or three

Since the definition of treatment outcomes follows the 2014 WHO Guidelines (20), as described in the ‘Research Protocol 6. Definition’, the change of a drug is allowed according to medical judgments, such as adverse drug reactions. However, the change of two or more drugs is considered ‘treatment failed’ and the participants will be withdrawn from the study.

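### Protocol 5.1.1 gives linezolid as an undated daily 600 mg dose, which contradicts the step-down in 5.1.2 from month 3 onward

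*Combined protocol and SAP*

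**What the plan says.** Protocol 5.1.1 (Study Drug) describes how linezolid and delamanid are labelled and delivered to sites. It makes designated pharmacists responsible for managing the drug, and dispensing must be recorded. It then has an entry for each product. The linezolid entry lists one strength ("Composition: linezolid 600mg") and, on its dosing line, says "Take one tablet (600mg) every day". The line has no start or end point, mentions no later change, and does not refer to another section.

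Protocol 5.1.2, under Group 2, sets out the investigational regimen. For linezolid it gives "600mg/day during the first two months" and then "300mg/day afterwards until the end of treatment". It adds one exception: when linezolid is restarted after a temporary stop for adverse events, "the dose reduction to 300mg is allowed even within two months of treatment". Treatment lasts 40 or 52 weeks, depending on when the sputum culture converts.

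The protocol summary and the SAP name linezolid as part of the regimen but give no dose, so they do not settle the difference.

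**The concern.** Taken at face value, the two sections prescribe different treatment for most of the investigational course. The product entry sits in the section that deals with labelling and dispensing, which is where a pharmacist might reasonably look for the dose. That section lists only a 600 mg tablet and does not say how a 300 mg dose is supplied, so nothing in it tells the reader that the dose changes.

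Two things would be at stake if the sections were followed differently:

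- **Safety.** Linezolid exposure would differ between participants assigned to the same arm. Adverse events of grade 3 and higher are a secondary outcome (Protocol 5.3), and Protocol 5.6.3 lists thrombocytopenia, leukopenia and neutropenia among the expected linezolid events.
- **Interpretation.** The investigational arm would contain more than one linezolid schedule, and the planned analyses would not separate them. Per-protocol status depends on weeks of treatment and a short list of violations, none of which is the linezolid dose level in the investigational arm (SAP 3.1). Adherence in SAP 3.5 counts dosing days. A participant on either schedule could therefore count as fully adherent and per-protocol.

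**Working it through.** The documents state no cumulative linezolid dose, so there is no figure to reproduce. The check compares the two sections and works out how far apart they are.

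**Side by side**

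| Period | Protocol 5.1.1 | Protocol 5.1.2, Group 2 |
|---|---|---|
| Months 1–2, uninterrupted | 600 mg/day | 600 mg/day |
| Month 3 to week 40 or 52 | 600 mg/day (no time limit given) | 300 mg/day |

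**Inputs**

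- Course length D, from Protocol 5.1.2: 40 weeks × 7 = 280 days, or 52 weeks × 7 = 364 days.
- Length of the first two months, M. The protocol does not give this in days. Assumption: 56 days (8 weeks), with a range up to 61 days.
- Full adherence and no interruption. The early-restart exception in 5.1.2 is therefore left out.

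**Formulas**

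- Total under 5.1.1 = 600 × D
- Total under 5.1.2 = 600 × M + 300 × (D − M)

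**40-week course**

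- 5.1.1: 600 × 280 = 168,000 mg = 168.0 g
- 5.1.2, M = 56: 600 × 56 + 300 × 224 = 33,600 + 67,200 = 100,800 mg = 100.8 g. Difference 67.2 g, ratio 168.0/100.8 = 1.67
- 5.1.2, M = 61: 600 × 61 + 300 × 219 = 36,600 + 65,700 = 102,300 mg = 102.3 g. Difference 65.7 g, ratio 168.0/102.3 = 1.64

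**52-week course**

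- 5.1.1: 600 × 364 = 218,400 mg = 218.4 g
- 5.1.2, M = 56: 600 × 56 + 300 × 308 = 33,600 + 92,400 = 126,000 mg = 126.0 g. Difference 92.4 g, ratio 218.4/126.0 = 1.73
- 5.1.2, M = 61: 600 × 61 + 300 × 303 = 36,600 + 90,900 = 127,500 mg = 127.5 g. Difference 90.9 g, ratio 218.4/127.5 = 1.71

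The length chosen for two months barely affects the result. The ratios measure the distance between two readings of the protocol. They do not estimate exposure in the trial or any effect on treatment success or adverse events.

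**The case against.** The strongest reply is that 5.1.1 is a product listing and was never meant as a regimen. Each entry gives brand, form, composition, dosing, storage and shelf life. It names no arm and no treatment duration, and levofloxacin and pyrazinamide are absent, so nobody could run the investigational regimen from it. Section 5.1.2 is the detailed regimen text, with phases, durations and an exception, and sites would probably follow it. Pharmacists are told to record dispensing, not to set the dose from that list, and the adherence formula in Protocol 8.6 presupposes a prescription. Labels and pharmacy instructions, which would settle the matter, are not among the documents.

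Most of this stands, and it limits the size of the point. It does not remove the contradiction. Whatever its purpose, the section that governs labelling and dispensing in this trial states a daily dose that differs from the regimen after month 2, and it neither limits that dose in time nor sends the reader elsewhere. Calling 5.1.2 the more detailed text also says nothing about which dose is right.

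Two stronger readings are tempting, and the documents support neither:

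- A reader might argue that the delamanid entry, "Take 100mg twice a day together with meal", matches 5.1.2 and so proves that 5.1.1 is a regimen instruction. Delamanid has one constant dose throughout, so a product listing and a regimen instruction would read the same. The match cannot tell them apart.
- A reader might infer that the twelve sites listed in SAP 4.2 did dispense different doses, so that the results come from a mixture of regimens. Nothing in the documents shows that any label, pharmacist or site relied on 5.1.1 alone.

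**Conclusion.** The point holds as an internal inconsistency: the protocol is wrong as written, and no design choice is in question. Sections 5.1.1 and 5.1.2 agree for uninterrupted treatment in months 1 and 2 and contradict each other from month 3 to the end of a 40- or 52-week course.

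The possible consequence is bounded. A label or pharmacist following 5.1.1 alone could produce a cumulative dose at most about 1.64 to 1.67 times (40 weeks) or 1.71 to 1.73 times (52 weeks) that under 5.1.2. To reach that bound, 5.1.2 would have to be ignored for the whole course, under the adherence and two-month assumptions set out above. Any real effect could be much smaller or absent.

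The point still deserves correction rather than a passing note. It concerns the dose of an investigational drug in the section used for dispensing, it bears on participant safety and on which regimen is being tested, and the planned analysis sets and SAP adherence measure would not reveal a difference in dose level.

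**What to change.** Reconcile Protocol 5.1.1 with 5.1.2 so that a single linezolid dosing statement applies, and have 5.1.1 refer to the regimen section instead of carrying its own undated dose. Check that study-drug labels and site dispensing instructions agree with the reconciled statement. Which dose is correct is for the sponsor and investigators to settle.

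The cost is a wording amendment, a note to site pharmacists and a check of labels. Because 5.1.1 already requires dispensing to be recorded, sites can also confirm from existing records what was given, without collecting new data. No change to the sample size or the analysis methods is needed.

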5.1.2. Multicenter, randomized, open-label, two arms, phase II/III clinical trial

- Once eligibility is confirmed and the subject consents for participation, he/she will be randomly assigned to the following two groups at 1:1.

① Group 1 (Control arm)

Treatment will be according to the 2014 Korean guidelines for the treatment of tuberculosis (19) and 2014 WHO guidelines (20). Treatment principles are summarized as follows.

- Combination of treatment regimen
 - Intensive phase regimen comprising four effective second-line anti-TB drugs (including an injectable) and pyrazinamide.
 - It is recommended that at least five active drugs be used, selected appropriately based on drug susceptibility testing (DST) results.
 - Example of regimen: pyrazinamide, a fluoroquinolone, cycloserine, prothionamide, and an injectable
 - Efforts should always be made to use a fluoroquinolone, preferentially use levofloxacin or moxifloxacin.
 - Cycloserine should be used preferentially, but when it is not possible para-aminosalicylic acid (PAS) could be used.
 - The medication like linezolid, delamanid, or bedaquiline can be added from the beginning of the treatment if the patient has a resistance to injectables. In addition, linezolid, delamanid, or bedaquiline can be used to fortify the regimen when the adverse drug reactions occur to other anti-TB drugs.
 - The usage and dosage follow 2014 Korean guidelines for the treatment of tuberculosis published by the Committee for the Revision of Korean Guidelines for Tuberculosis and the Korea Centers for Disease Control and Prevention (19) but not limited to it.

Type of Drug	Dose		
	Usual dose	Maximal dose	Usage
Ethambutol	15-20mg/kg	1600mg	Once, before or after

Confidential

MDR-END v14.0, 20Mar2020

			meal
Kanamycin Amikacin Streptomycin Capreomycin	15mg/kg, < 50 years 10mg/kg, ≥ 50 years	1000mg, < 50 years 750mg, ≥ 50 years	Once
Cycloserine	500mg, < 50 kg 750mg, 50-70 kg 750-1000mg, >70 kg	1000mg	Once or divide in two, before or after meal (best to take on an empty stomach)
Prothionamide	500mg, < 50 kg 750mg, 50-70 kg 750-1000mg, >70 kg	1000mg	Once or divide in two, after meal
PAS	150mg/kg	12g	Divide in two or three after meal

- Treatment duration

- Intensive phase is recommended to be a minimum of 8 months.
- Total treatment duration is recommended to be 20 to 24 months.

② Group 2 (Investigational Group)

Regimen consists of only oral medication using delamanid, linezolid, levofloxacin, and pyrazinamide, for nine or twelve months.

- Treatment duration

- A total of 9 months (40 weeks) when sputum culture conversion to negative occurs within three months of treatment
- A total of 12 months (52 weeks) when sputum culture conversion to negative occurs between 3 and 6 months of treatment

- Combination of treatment regimen

- Delamanid, 200mg/day (100mg bid)
 - Use for the entire treatment period unless it must be stopped for reasons such as adverse events.
- Linezolid
 - 600mg/day during the first two months
 - 300mg/day afterwards until the end of treatment

Confidential

MDR-END v14.0, 20Mar2020

- If linezolid re-administration is required after temporary discontinuation due to adverse events, the dose reduction to 300mg is allowed even within two months of treatment.
- Levofloxacin
 - $\leq 50\text{kg}$, 750mg/day
 - $>50\text{kg}$, 1000mg/day
 - Can be reduced or substituted with moxifloxacin due to reasons such as adverse events, and at this time, QT prolongation should be observed closely. Also, this substitution will not be considered as a drug change since both are fluoroquinolones of similar potency.
 - Once a day
- Pyrazinamide
 - $<50\text{kg}$, 1000mg/day
 - 50-70kg, 1500mg/day
 - $>70\text{kg}$, 2000mg/day
 - Can be reduced due to adverse event. Even if pyrazinamide resistance is discovered on the phenotypic drugs susceptibility testing after commencing treatment, it can be continued (20).
 - Once or divide in two or three

Since the definition of treatment outcomes follows the 2014 WHO Guidelines (20), as described in the ‘Research Protocol 6. Definition’, the change of a drug is allowed according to medical judgments, such as adverse drug reactions. However, the change of two or more drugs is considered ‘treatment failed’ and the participants will be withdrawn from the study.

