6.4. Treatment Outcome Definitions

Definitions of treatment outcomes refer to 2014 WHO Guidelines (20). For investigational group, 6 months will be considered as intensive phase.

<Definitions of treatment outcomes for drug-resistant patients>

TREATMENT OUTCOME	DEFINITION
Cured	Treatment completed as recommended by the national policy without evidence of failure AND three or more consecutive cultures taken at least 30 days apart are negative after the intensive phase. ^a
Treatment completed	Treatment completed as recommended by the national policy without evidence of failure BUT no record that three or more consecutive cultures taken at least 30 days apart are negative after the intensive phase. ^a
Treatment failed	Treatment terminated or need for permanent regimen change of at least two anti-TB drugs because of: 
•Lack of conversion^b by the end of the intensive phase^a; or•Bacteriological reversion^b in the continuation phase after conversion^b to negative; or•Evidence of additional acquired resistance to fluoroquinolones or second-line injectable drugs; or•Adverse drug reactions.

Died	A patient who dies for any reason during the course of treatment.
Lost to follow-up	A patient whose treatment was interrupted for two consecutive months or more.
Not evaluated	A patient for whom no treatment outcome is assigned. (This includes cases “transferred out” to another treatment unit and whose treatment outcome is unknown).
Treatment success	The sum of Cured and Treatment completed.

^a For Treatment failed, lack of conversion by the end of the intensive phase[†] implies that the patient does not convert within the maximum duration of the intensive phase[†] applied by the programme. If no maximum duration is defined, an 8-month cut-off is proposed. For regimens without a clear distinction between intensive and continuation phases, a cut-off eight months after the start of treatment is suggested to determine when the criteria for Cured, Treatment completed and Treatment failed start to apply. (†For investigational group, 6 months will be considered as intensive phase.)

^b The terms “conversion” and “reversion” of culture as used here are defined as follows :

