10.1. Sample size justification

The hypothesis of this study is that the treatment success rate at 24 months after the initiation of treatment for MDR TB using the new regimen including new anti-TB drugs will not be inferior to conventional treatment regimens. (Non-inferiority test)

Presumptions when calculating sample size are as follows.

- 1) Level of significance, $\alpha = 0.025$ (one-sided test)
- 2) Type 2 error (β) set at 0.20 to maintain 80% for power of the test
- 3) Subject no. ratio (control arm : investigational arm) = 1 : 1
- 4) Primary outcome: treatment success rate at 24 months after the initiation of treatment
- 5) The hypothesis of the study is as follows.
 - ① Null hypothesis: Four drug regimen treatment success rates at 24 month are inferior to conventional treatment outcomes. ($H_0 : P_T - P_C \leq \delta$)
 - ② Alternative hypothesis: Four drug regimen treatment success rates at 24 month are not inferior to conventional treatment outcomes. ($H_1 : P_T - P_C > \delta$)

Based on the study result of Kwak et al, 'Changes in treatment outcomes of multidrug-resistant tuberculosis, Int J Tuberc Lung Dis 19(5):525-530'(3), presuming 24 month treatment success rate of control arm as 80% and 24 month treatment success rate of investigational arm as 90%, the non-inferiority margin (δ) is -0.10 which is regarded as non-inferior when the difference is less than 10% between the two arms. The number of study subjects is 48 per arm.

In addition, reflecting 1) proportion of fluoroquinolone-susceptible MDR-TB among participants with positive Xpert MTB/RIF assay of 50%, and 2) anticipating 5% lost to follow-up, the final number of participants is calculated as $N/(0.50*0.95)$ resulting in 102 persons per arm, 204 in total.

If a participant withdrew for any reasons within two weeks after enrollment, the participant will be replaced. Considering the number of replaced participants, the enrollment accrual ceiling is 220 persons maximum.

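### The rule that replacing levofloxacin with moxifloxacin is not a drug change is written for the investigational arm only, so on a literal reading the two arms count treatment failure differently

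*Combined protocol and SAP*

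**What the plan says.** Four places bear on this.

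- **Protocol 5.1.2, Group 2 (investigational), levofloxacin entry.** Levofloxacin may be replaced by moxifloxacin for reasons such as adverse events, and "this substitution will not be considered as a drug change since both are fluoroquinolones of similar potency". The paragraph closing the Group 2 text adds that a change of two or more drugs is treatment failure and leads to withdrawal. It does not require the change to be permanent and lists no qualifying causes.
- **Protocol 5.1.2, Group 1 (control).** A fluoroquinolone should be used, and sites should "preferentially use levofloxacin or moxifloxacin". Nothing is said about how a later move between the two is counted. Linezolid, delamanid or bedaquiline may be added after adverse reactions, also without a counting rule.
- **Protocol 6.4, both arms.** Failure is treatment terminated or "need for permanent regimen change of at least two anti-TB drugs because of" one of four listed causes, adverse drug reactions among them. The only arm-specific note concerns the length of the intensive phase.
- **Protocol 5.2, both arms.** Stopping a drug is not a drug change.

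The SAP (3.1, 3.2 and 3.6.1) adds no rule on counting drug changes.

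**The concern.** The exemption is a counting rule for the primary outcome, but it sits in one arm's dosing text. Its stated reason, similar potency, concerns the two drugs and not the arm. The protocol can write such rules for everyone: the one on stopping, in 5.2, has no arm restriction. That an exemption was needed implies that without it a swap would count as a change.

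On the literal text, then, two participants with the same history (this swap plus one other permanent change for a listed cause) are scored differently by arm. The trial is open-label and drug changes follow medical judgment, so whoever classifies a control with a swap must choose a rule, possibly knowing the arm. The number analysed is small, so one reclassified participant moves the difference by about 2 points against a margin of 10.

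**Working it through.** **1. The same event under each arm's text**

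| Event | Investigational | Control |
|---|---|---|
| Levofloxacin to moxifloxacin only | exempt: 0 changes | no rule; literally 1 change, not failure |
| The same swap plus one other permanent change for a listed cause | 1 change: not failure | literally 2 changes: failure |
| The same swap plus stopping another drug | 0 changes | literally 1 change, not failure |

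Only the second row differs in outcome. The asymmetry therefore reaches only controls who have exactly one other countable change and who would otherwise have been successes.

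**2. The plan's own figure**

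Inputs from Protocol 10.1: control 80%, investigational 90%, one-sided 0.025, power 80%, allocation 1:1, and "the non-inferiority margin (δ) is -0.10".

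- n = [0.80×0.20 + 0.90×0.10] × (1.960 + 0.842)² / (0.10 + 0.10)² = 0.25 × 7.849 / 0.04 = 49.06, or 50 per arm. The plan states 48.
- Power at 48: Φ(0.20/√(0.25/48) − 1.960) = Φ(0.811) = 79.1%.
- Inflation: 48/(0.50 × 0.95) = 101.05, or 102 per arm and 204 in total, as stated.

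The stated size is close to the formula and is not in dispute.

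**3. Number analysed**

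102 × 0.50 (the fluoroquinolone-susceptible share) = 51 per arm. The 5% loss is not removed here because Protocol 10.2 scores loss during treatment as failure. One participant is 1/51 = 1.96 points.

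**4. Effect of the asymmetry alone**

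Let m be the share of all controls scored as failures only because the swap was their second change. The documents give no figure for m, so it is an assumption. Scored control success is p_C − m, and the expected difference is p_T − p_C + m. At the margin that is −10 points + m.

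Non-inferiority is declared when

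p̂_T − p̂_C − 1.960 × √[p̂_T(1 − p̂_T)/51 + p̂_C(1 − p̂_C)/51] > −0.10.

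The documents name no interval method, so the Wald bound is also an assumption. Summing exact binomial probabilities over all outcomes gives:

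| m | Controls (51 × m) | True 70% vs 80% | True 80% vs 90% |
|---|---|---|---|
| 0 | 0 | 2.7% | 2.8% |
| 0.5% | 0.3 | 3.1% | 3.3% |
| 1% | 0.5 | 3.5% | 3.8% |
| 2% | 1.0 | 4.5% | 5.0% |
| 3% | 1.5 | 5.6% | 6.5% |

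The baseline already exceeds 2.5% because of the Wald bound. The part due to m is about 0.4 to 3.7 points over this range.

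Cross-check by normal approximation at 48 per arm, 70% vs 80%: 2.5%, 3.2%, 4.1% and 5.2% at m = 0, 1%, 2% and 3%.

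**The case against.** The strongest reply is that no section says a control swap counts. The control regimen is defined largely by class: its example lists a fluoroquinolone without naming one, so moving between two preferred members of the class can fairly be read as no regimen change. The investigational regimen names levofloxacin, so leaving it needs an explicit rule. Protocol 3.1 also reports no difference between the two drugs in culture conversion at three months (88.3% and 90.5%). This stands to the extent that the control text is silent rather than explicitly stricter. It does not remove the gap, because Protocol 6.4 has no exemption and the only one written is confined to one arm.

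A reader might go further and infer that the drug-change rules as a whole favour non-inferiority. The documents do not support that. If placement under Group 2 makes a sentence arm-specific, the two-drug failure rule there is arm-specific too. It lacks the permanence and the listed causes that 6.4 requires, so it could make failure easier to reach in the investigational arm. How drugs added in control are counted is also open.

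A reader might also take a single affected share, such as 2%, as an estimate. It is not one. The affected group is narrow, it may be empty, and with none affected there is no effect.

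**Conclusion.** The point holds in limited form. The exemption is stated for the investigational arm only, control is silent, and the common failure definition has no exemption. Applied literally, identical changes give different primary outcomes by arm, and this element alone can only lower control success.

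Its size is conditional: about 2 points on the difference per affected control, and a one-sided error at the margin of 3.1–6.5% instead of 2.7–2.8% if 0.5% to 3% of controls are affected. That rests on 51 analysed per arm, a Wald bound, true control success of 80% (the planning value) to 90%, and an affected share that the documents do not give. Neither a bias that has in fact occurred nor a net direction across all the drug-change rules is shown.

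**What to change.** Reconcile the Group 1 and Group 2 texts of Protocol 5.1.2 with Protocol 6.4. State in 6.4, and repeat in SAP 3.6.1, one drug-change counting rule for outcome classification in both arms, and classify the primary outcome by it. Carry over the existing levofloxacin/moxifloxacin exemption with its present scope, applied identically in both arms; widening or narrowing it would also alter how the investigational arm is scored. The same rule should settle whether a counted change must be permanent and for a listed cause, and how drugs added in control are counted, since 5.1.2 and 6.4 now differ or are silent there.

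The rule concerns classification only and changes no treatment. Because 5.1.2 and 8.7 tie withdrawal to treatment failure, the amendment should say explicitly how those passages relate to it. The cost is a sentence in each document and no new data.
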